7.2.2.1 Pre-dose Procedures for Dose Titration Period Visits (Study APD811-003 Placebo Subjects)

- Vital signs according to Table 2
- Safety ECG at Weeks 1 to 9 according to Table 2
- Assessment of clinical worsening
- WHO/NYHA FC assessment
- Clinical laboratory tests (to include hematology, coagulation parameters, serum chemistry, and urinalysis) at Weeks 2, 5, and 9
- Serum hCG pregnancy test (females only) at Week 5
- Record AEs
- Record concomitant medications

7.2.2.2 Post-dose Procedures for Dose Titration Period Visits (Study APD811-003 Placebo Subjects)

- Study drug administration
- Vital signs: every hour through the first 4 hours
- Safety ECG 2 hours post-dose at Weeks 1 to 9 according to Table 2
- Record AEs
- Record concomitant medications

7.2.3 Study Procedures for the Treatment Period – All Subjects (For Both Immediate-release and Extended-release Formulations)**7.2.3.1 Study Procedures M1-M3 (Study APD811-003: Placebo-treated Subjects) Q3 Months (Study APD811-003: Placebo- and Ralinepag-treated Subjects; Subjects who Switched to the XR Formulation)**

- Safety ECG according to Section 6.5.2 and Table 1 and Table 2.
- Clinical laboratory tests (to include hematology, coagulation parameters, serum chemistry, and urinalysis) according to Section 6.10 and Table 1 and Table 2.
- Serum hCG pregnancy test (females only) according to Section 6.10 and Table 1 and Table 2
- Vital signs
- Study drug administration
- 6MWT
- BNP/NT-proBNP according to Section 6.10 and Table 1 and Table 2
- Assessment of clinical worsening
- WHO/NYHA FC assessment
- Dose escalation assessment according to according to Table 1 and Table 2
- Record AEs
- Record concomitant medications

7.2.3.2 Study Procedures - Year 1 or Year 2

- RHC – according to Table 1 and Table 2 (see study RHC manual)

7.2.3.3 Switch to XR Ralinepag and Dose Titration

At 1 of the regular quarterly visits, as outlined in Section 7.2.3.1, in addition to the regularly scheduled procedures, subjects will be given new dosing cards with an XR formulation of ralinepag. Dose-switching will occur as outlined in Table 5, and titration will occur as

described in Section 5.6.2.1 via weekly telephone calls until the next regularly scheduled quarterly visit, at which time the subject will resume procedures described in Section 7.2.3.1.

7.2.4 End of Study Visit – All Subjects

- Physical exam
- Safety ECG according to Section 6.5.2 and Table 1 and Table 2
- Clinical laboratory tests (to include hematology, coagulation parameters, serum chemistry, and urinalysis) according to Section 6.10 and Table 1 and Table 2
- Serum hCG pregnancy test (females only)
- Vital signs
- 6MWT
- Assessment of clinical worsening
- WHO/NYHA FC assessment
- Record AEs
- Record concomitant medications

7.2.5 28-day Follow-up – All Subjects

- WHO/NYHA FC assessment
- Assessment of clinical worsening
- Record AEs
- Record concomitant medications

8 DATA MANAGEMENT

8.1 DATA COLLECTION

All data (ECGs, clinical laboratory data, and all other study-related data) will be collected according to the Sponsor or CRO's SOPs.

Upon database lock, to include resolution of all queries, the CRO (if applicable) will provide statistical analysis software transfer datasets to the Sponsor and biostatistician for analysis using secure electronic data transfer per the Sponsor's specifications.

8.2 DATA CODING

8.2.1 *Adverse Events*

AEs will be coded using the MedDRA and tabulated, including categorical information of interest, such as onset and resolution times, time of onset relative to dose, severity at onset, maximum severity, causal relationship to study drug, and action taken. Whenever possible, a constellation of signs and symptoms should be recorded as a unifying diagnosis (eg, self-limited fever, runny nose, cough, and scratchy throat should be captured as an upper respiratory infection rather than by the individual signs and symptoms). As there is no Screening Period in this study and subjects will enter the study on active treatment, all AEs that occur after the first dose of study drug will be considered treatment emergent.

8.2.2 *Concomitant Medications*

Due to the variability in how medications are recorded, a standard naming convention is required in order to tabulate these data effectively. A common method of standardization is to categorize medications by their Preferred Term. In order to do this, medications will be coded using the WHO Drug Dictionary.

9 PLANNED STATISTICAL METHODS

After the last subject enrolled in APD811-007 completes approximately 6 months of treatment, a cumulative all-subject data analysis will be performed.

The statistical analysis of the data obtained from this study will be the responsibility of the Sponsor. Details of the statistical analyses will be included in a separate Statistical Analysis Plan, which will be finalized before database lock. If, after the database has been locked, changes are made to the pre-specified Statistical Analysis Plan, the changes will be listed along with an explanation as to why they occurred in the Clinical Study Report.

9.1 ANALYSIS POPULATIONS

Safety Population:

This population will include all subjects who received at least 1 dose of the study drug in this extension study.

Modified Intent-to-treat Population:

The analyses of all efficacy variables will use the Modified Intent-to-Treat Population. This population consists of all subjects randomized who received at least 1 dose of study drug in the extension study, have a baseline measurement, and have at least 1 measurement after entry into the extension study. The Last Observation Carried Forward approach will be used to impute missing values.

9.2 STATISTICAL METHODS**9.2.1 Safety Analysis**

Safety is the primary analysis for this extension study. All subjects who receive study drug in the extension study will be evaluated for safety. Long-term safety and tolerability of ralinepag will be assessed by clinical and statistical review of all relevant safety parameters, including AEs, laboratory values, vital signs, and ECG findings.

9.2.1.1 Demographics and Baseline Characteristics

All baseline subject characteristics for demographic data (age, height, weight, race), medical history (abnormalities only), physical examination (abnormalities only), and concomitant medications at entry in Study APD811-003 and also at entry in this extension study will be listed for all subjects. Demographic data will be summarized and tabulated. Continuous variables will be summarized using number of observations, mean, standard deviation, median, minimum, and maximum. Frequencies and percentages will be reported for all categorical data.

9.2.1.2 Adverse Events

The AEs will be coded using the most current MedDRA and tabulated, including categorical information of interest, such as onset and resolution times, time of onset relative to dose, severity at onset, maximum severity, causal relationship to study drug, and action taken.

All AEs will be listed by subject and will be summarized and expressed in terms of maximum severity and relationship to study drug.

9.2.1.3 Physical Examinations

Physical examination results (abnormalities only) will be collected.

9.2.1.4 Vital Signs

Individual vital sign measurements will be listed by measurement time and summarized using descriptive statistics. Summary statistics will also be provided for change from baseline in vital sign measurements.

9.2.1.5 Clinical Laboratory Values

Individual laboratory values will be listed by visit and summarized using descriptive statistics. Summary statistics will also be provided for change from Baseline in laboratory values. Shift tables from baseline to the last extension study visit will also be produced for the laboratory assessments based on the categories of Low, Normal, and High. A clinically significant change from baseline may be recorded as an AE if deemed appropriate by the Investigator or Sponsor.

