Overall, there were no deaths or SAEs, and all AEs were mild or moderate with the exception of 1 Grade 3 adverse drug reaction (ADR). In both the fasted and fed states, the majority of subjects experienced at least 1 AE, most of which were ADRs, and the number and percentage of AEs and ADRs were comparable. The majority of AEs were transient in nature and had resolved by the end of the study. The profile of AEs from both fasted and fed subjects were consistent with the reference safety information for ralinepag and other prostacyclin receptor agonists, with notable exceptions of the AEs of Grade 3 increased transaminases and Grade 1 ventricular extrasystoles.

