8 GENERAL CONSIDERATIONS FOR DATA ANALYSES

All data included in each data cut will be listed. In general, listings will be sorted by subject number and scheduled assessment (if applicable) or the visit date. Listings will include assessment date, assessment time (if available), and study day. The study day is calculated as the assessment date minus the date of the first ralinepag dose in the APD811-007 study. For data collected on a fixed schedule, the assessment identifier will also be included on the listing.

In general, the data will be summarized by scheduled (nominal) visits. For all presentations of the summary tables, the data will be presented by treatment group of the parent study and overall.

For continuous variables, the summary statistics will include the mean, standard deviation, median, minimum, and maximum. Minimums and maximums will be expressed using the level of precision in which the variable was collected. All other statistics will be rounded, using an additional decimal point. For discrete variables, summaries will include the frequency and

percent in each category. Percentages will be rounded to 1 decimal point. Whenever practical, categories of discrete variables will be ordered and labeled as they appear in the electronic Case Report Form, and all categories represented on the electronic Case Report Form will be included in summaries, even when they do not apply to any subjects in the study.

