8.4 ASSESSMENT WINDOWS

For efficacy and safety assessments, baseline is defined as the last measurement prior to the first dose of ralinepag in the APD811-007 study.

Summary analyses will usually be based on the scheduled (nominal) visits with no visit windows applied. If appropriate, hemodynamic parameters will only be summarized by the Baseline and post-Baseline Visits of APD811-007.

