11.3 CLINICAL LABORATORY TESTS

The laboratory data will be listed by subject number and treatment group in the parent study, including all hematology and clinical chemistry parameters by visit. The listings will include the collection date/times (day), laboratory test, and results. The normal laboratory reference ranges will be included in the listings. A designation for low (L) or high (H) will be included for those laboratory values that are outside the relevant normal range. The listing of urinalysis and coagulation will also be presented by subject number and treatment group in the parent study and will include each scheduled and unscheduled urinalysis assessment. The laboratory sample collection date/time (day), laboratory test, normal range, designation for high or low, and analysis visit will be provided for each assessment, as well as the result of the test.

For hematology, clinical chemistry, and coagulation parameters, the original values and their changes from baseline (defined as the last measurement prior to the first dose of ralinepag in the APD811-007 study) will be summarized for each analysis visit by the treatment group in the parent study and overall. Shift tables for hematology and clinical chemistry will also be provided. For urinalysis results, the number (percent) of subjects within each category will be summarized for all analysis visits by treatment group in the parent study and overall.

Pregnancy test results for female subjects will be organized by treatment group in the parent study and listed by subject number and did the subject become pregnant during the study (yes/no).

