12 CHANGES FROM ANALYSIS PLANNED IN THE PROTOCOL

For the final analysis, the following changes have been made to the analyses that are described in the protocol:

- Safety Population will be used for all summaries (protocol Section 9.1 specifies modified Intent-to-Treat Population for efficacy analyses).
- The protocol separated the primary objective and secondary objectives. The analyses will be based on efficacy and safety, not specifically separating the primary and secondary objectives.
- Protocol Section 6.2 states medical and social history would be updated at Baseline in Study APD811-007. These updates were not collected.
- No imputation will be performed for missing efficacy values (protocol Section 9.1 specifies Last Observation Carried Forward imputation for efficacy missing values).
- Baseline for change from baseline in efficacy values will be the APD811-007 baseline value (protocol Section 9.2 specifies the Day 1 pre-dose measurement in Study APD811-003 as the main baseline, with Day 1 of Study APD811-007 as baseline for a secondary analysis).
- Follow-up vital status (mortality) was not collected.
- Local results of BNP/NT-proBNP are not available.

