13 APPENDICES**13.1 LIST OF TABLES**

Table titles suggested here may be altered or edited as appropriate by the clinical data programmers while maintaining the original intent of the summary.

Table Number	Table Title
14.1.1	Summary of Subject Accountability
14.1.2	Summary of Ralinepag Exposure
14.1.3	Summary of Ralinepag Exposure in APD811-003 and APD811-007 Studies
14.1.4	Summary of Demographics
14.1.5	Summary of Baseline Characteristics
14.1.6	Summary of PAH History
14.1.7	Summary of Study Entry Criteria
14.1.8	Summary of Ralinepag Dosing
14.1.9.1	Summary of Concomitant Medications Ongoing from the Previous Study
14.1.9.2	Summary of Concomitant Medications Added in Study APD811-007
14.2.1.1	Summary and Analysis of Clinical Worsening
14.2.1.2	Summary of 6MWD (meters) by Visit
14.2.1.3	Summary of WHO Functional Class by Visit
14.2.1.4	Summary of Hemodynamics by Visit
14.2.1.5	Summary of BNP and NT-proBNP by Visit
14.3.1.1	Overall Summary of Adverse Events
14.3.1.2	Summary of Adverse Events by System Organ Class and Preferred Term
14.3.1.3	Summary of Adverse Events by Preferred Term
14.3.1.4	Summary of Serious Adverse Events by Preferred Term
14.3.1.5	Summary of Severe Adverse Events by Preferred Term
14.3.1.6	Summary of Serious Adverse Events Related to Ralinepag by Preferred Term
14.3.1.7	Summary of Adverse Events Related to Ralinepag by Preferred Term
14.3.1.8	Summary of Adverse Events Leading to Permanent Discontinuation of Study Drug by Preferred Term
14.3.1.9	Summary of Adverse Events Adjusted for Length of Ralinepag Exposure
14.3.2.1	Listing of Deaths
14.3.2.2	Summary of Deaths
14.3.2.3	Listing of Serious Adverse Events
14.3.4.1	Summary of Hematology Data
14.3.4.2	Summary of Hematology Shifts from Baseline
14.3.4.3	Summary of Clinical Chemistry Data
14.3.4.4	Summary of Clinical Chemistry Shifts from Baseline
14.3.4.5	Summary of Urinalysis Data
14.3.4.6	Summary of Coagulation Data

Table Number	Table Title
14.3.4.7	Summary of Vital Signs
14.3.4.8	Summary of Electrocardiogram Parameters

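### Laboratory shift tables compare baseline with the last visit in Low/Normal/High; the SAP states no time point or grade, and no worst-value or graded laboratory table is planned

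*Protocol*

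**What the plan says.** **The shift rule.** Protocol 9.2.1.5 contains the only definition in either document: "Shift tables from baseline to the last extension study visit will also be produced for the laboratory assessments". It sets three categories, Low, Normal and High, with no severity grades. SAP 11.3 says "Shift tables for hematology and clinical chemistry will also be provided" and gives no time point, category or worst-value rule. The titles in SAP 13.1 add nothing; Table 14.3.4.4, for example, is "Summary of Clinical Chemistry Shifts from Baseline".

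**The SAP's defaults.** SAP 8 states: "In general, the data will be summarized by scheduled (nominal) visits". SAP 8.4 adds: "Summary analyses will usually be based on the scheduled (nominal) visits with no visit windows applied". SAP 12 opens with "For the final analysis, the following changes have been made to the analyses that are described in the protocol", and its list does not mention the laboratory shift tables.

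**Other routes by which a laboratory abnormality can appear.**
- SAP 11.3 summarises values and changes at each visit, and SAP 8 includes the minimum and maximum among the summary statistics.
- SAP 11.3 lists individual results with reference ranges and flags those out of range as L or H.
- Protocol 6.12.1 counts abnormal laboratory findings among possible adverse events, and 6.12.4 grades adverse events by CTCAE v4.03. Protocol 9.2.1.5 leaves it to the investigator or sponsor whether a clinically significant change is recorded as one.

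**Background.** Protocol 1.1.3 describes the adverse event profile of the XR tablet study in healthy subjects as in line with what was known, "with notable exceptions of the AEs of Grade 3 increased transaminases and Grade 1 ventricular extrasystoles". Under Protocol 5.6.2.1, all subjects in this study switch to XR.

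**The concern.** Long-term safety is the primary objective, and the shift tables are the only planned laboratory tables that count subjects moving out of range in hematology and chemistry. A comparison of baseline with the last visit ignores everything in between. With three categories, it also cannot separate a small excursion above the limit from a large one. The reader of the study report could therefore see few or no shifts in a parameter although some subjects had marked elevations. For the liver in particular, no table shows how many subjects passed a given multiple of the upper limit, or whether bilirubin rose at the same time.

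The timing of visits adds to this. After the XR switch, titration is guided by weekly telephone calls until the next quarterly visit (Protocol 7.2.3.3). A blood sample drawn in that interval would be unscheduled, and summaries by nominal visit would usually leave it out.

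**Working it through.** The documents give no figure on this point, so there is none to reproduce. The check applies the rule to constructed cases.

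**1. Four made-up ALT courses** (multiples of the upper limit; baseline 0.6, then four visits; High means above 1):

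| Course | Post-baseline values | Baseline to last visit | By nominal visit | Worst value |
|---|---|---|---|---|
| A, severe, resolved | 0.7, 7, 0.8, 0.7 | Normal to Normal | High at 1 of 4 | 7 |
| B, mild, persistent | 1.1, 1.2, 1.2, 1.2 | Normal to High | High at 4 of 4 | 1.2 |
| C, severe at the end | 0.7, 0.7, 0.8, 7 | Normal to High | High at 1 of 4 | 7 |
| D, severe, partly resolved | 7, 3, 1.5, 1.1 | Normal to High | High at 4 of 4 | 7 |

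Under the last-visit rule, A is not counted, and B, C and D fall in one cell. A table by nominal visit would count A at its peak, but still without a grade. A worst-value table in three categories would put all four in High. Only worst value and grade together separate A, C and D from B.

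**2. Chance that a one-visit rise is counted.** Assumption, not trial data: the value is High at exactly one of k quarterly visits, equally likely at each, and every visit has a recorded value.

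P(counted in the last-visit table) = 1/k. 
P(no Normal-to-High shift shown, given m such subjects) = (1 − 1/k)^m.

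| Follow-up | k | 1/k | No shift shown, m = 3 |
|---|---|---|---|
| 1 year | 4 | 0.250 | 0.75³ = 0.42 |
| 2 years | 8 | 0.125 | 0.875³ = 0.67 |
| 3 years | 12 | 0.083 | (11/12)³ = 0.77 |
| 5 years | 20 | 0.050 | 0.95³ = 0.86 |

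A table of the worst post-baseline value counts such a rise with probability 1, provided that it was measured and recorded.

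**3. What the by-visit summary shows.** Suppose that one subject's ALT goes from 25 to 250 U/L at a scheduled visit. The visit mean moves by 225/N: 7.5 U/L for N = 30, 5.0 for N = 45, 3.75 for N = 60. The visit maximum is at least 250 and the maximum change at least +225, so the value is visible as an extreme. The table does not say how many subjects had such values.

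**4. Which values are in the database.** Protocol 6.10 and footnote e of Tables 1 and 2 move quarterly laboratory tests to local laboratories, as the investigator sees fit, once the cumulative analysis has been done. From then on, the local values to be databased are the abnormal ones judged clinically significant. The assumption in step 2 that every visit has a value therefore fails for later follow-up. A normal last-visit value may be absent, and SAP 8.2 rules out imputation. Depending on how the last visit is taken, the subject either drops out of the table or is represented by an earlier value, possibly the abnormal one. The figures in step 2 describe the rule with complete quarterly data; they do not predict this study's table.

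**The case against.** The strongest reply is that severe values are not hidden. The by-visit tables carry the maximum of values and changes, the listings flag out-of-range results, and laboratory findings can be adverse events with a CTCAE grade and a separate table for severe events. With about 60 subjects and no concurrent control, reading the listings subject by subject is feasible. The SAP is also the later and more detailed plan. It does not repeat the last-visit rule, and its nominal-visit default could be read to cover the shift tables.

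Much of this stands. A reader might infer that a transient severe rise disappears from the analysis altogether. The documents do not support that: at a scheduled visit it appears as a maximum, and it can appear in the listings and adverse event tables. Nor do they settle that the final shift tables will use the last visit, although SAP 12 declares no departure from that rule. And a rise only partly resolved at the last visit is still counted as High.

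What the reply does not remove is narrower. A maximum shows one extreme, not the number of subjects. Listings are not counts. The adverse event route depends partly on judgement. On the nominal-visit reading, severe and marginal elevations still share a cell, and unscheduled values are still usually outside the summary. If the two documents leave the rule open, that is itself a reason to state it.

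**Conclusion.** The point holds as a gap in the shift tables and in the SAP's specification of them. It is not a failure to capture laboratory safety data. Followed as written, the protocol's rule does not count an abnormality that has returned to range by the last visit, and it does not distinguish severity in those that persist. Under the one-visit assumption with complete quarterly data, the chance of being counted is 25% at 1 year and 5% at 5 years. No planned table counts subjects by severity of laboratory abnormality or pairs transaminases with bilirubin.

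It is tempting to cite the Grade 3 transaminase event in the XR study as a case that this plan would miss. The documents do not support that use. The event occurred in healthy subjects in another study and was captured there as a graded adverse event. The protocol calls most of that study's events transient but does not say so of this one. It is a reason to display severity, not evidence about transience.

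This is a worthwhile, inexpensive improvement in the reporting of the primary objective.

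**What to change.** In SAP 11.3, and for Tables 14.3.4.2 and 14.3.4.4:

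- Define the shift as baseline to worst on-treatment value, including unscheduled and local values, by CTCAE v4.03 grade where a grade exists and by Low/Normal/High otherwise.
- Keep baseline to last visit as a second panel, so that the analysis in Protocol 9.2.1.5 is still reported.
- Add one table counting subjects with ALT or AST above 3 and above 5 times the upper limit, and with concurrent bilirubin above 2 times the upper limit. These are display thresholds only.
- Show the number of subjects and visits with laboratory data. Footnote that after the cumulative analysis only abnormal local values judged clinically significant are databased; a worst-value table inherits that selection.

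The cost is SAP wording, two reprogrammed tables and one new one, with no new procedures. Protocol 6.10 provides for reference ranges to be stored with the local values. The availability of local results should be confirmed first, because SAP 12 reports that local BNP/NT-proBNP results are not available. Worst-value shifts will look less favourable than last-visit shifts, and the text of the report should say why.
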